Secondary Aim (4): Does location of the peripheral intravenous catheter placement affect the pain that adult patients experience with peripheral IV cannulation?

D. Enrollment and Withdrawal

D.1 Inclusion Criteria

1. **Describe the criteria that define who will be included in the study as a numbered list:**

1. Adults ages 18 to 99
2. Non-pregnant women and men
3. Adults that are able to consent
4. Patients requiring intravenous catheter insertion for their operation/procedure

D.2 Exclusion Criteria

1. **Describe the criteria that define who will be excluded in the study as a numbered list:**

1. Patients with Raynaud's syndrome, sickle cell disease, and/or extreme sensitivity to cold
2. Patients with a break or an abrasion on the skin where the Buzzy device would be placed
3. Patients with nerve damage affecting the extremity where the peripheral intravenous catheter would be placed

2. **Describe in detail how the eligibility criteria will be assessed and satisfied (e.g., medical record review, physical examination):** Based on the pre-operative history and physical exam performed by the CA-1 (PGY-2) anesthesiology resident (co-investigator of study).
3. **State who will determine eligibility. Note that those who are designated to determine eligibility must have appropriate training, expertise, and oversight, for example a physician PI or Co-I on a biomedical**

study: PI (anesthesiology attending) and Co-I (CA-1 (PGY-2) anesthesiology resident). These will be the physicians who will be taking care of these subjects.

4. **Can study subjects participate in another research study while participating in this research study:**
 Yes No

D.3 Withdrawal of Subjects

1. **Describe anticipated circumstances under which subjects will be withdrawn from the research without their consent:** None
2. **Describe procedures that will be followed when subjects withdraw or are withdrawn from the research, including the possibility of partial withdrawal from study intervention with continued data collection:**
There will be no partial withdrawal from the study. Either the patient will take part in the study, which is just for the duration of the peripheral intravenous catheter insertion and the questionnaire that will take place before and after the procedure, or the patient will not take part in the study.
3. **Describe any necessary safety precautions to be applied to subjects who withdraw or are withdrawn (tapering drug doses, evaluative x-ray, etc.):** or N/A

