Co-I's will be CA-1 (PGY2) anesthesiology physician residents at St. Elizabeth's Medical Center. They all will have approximately the same level of performing informed consent and of performing peripheral intravenous catheter insertion. The PI will be an anesthesiology attending physician who will ensure that all of the Co-I's are well versed on the study protocol, informed consent process, use of intradermal lidocaine, use of Buzzy® device, and the peripheral intravenous catheter insertion technique. The Co-I's will utilize the Operating Room Scheduling Board to learn about the scheduled patients for the day. All of these patients will require a peripheral intravenous catheter for the scheduled procedure. If the patient does not yet have a working peripheral intravenous catheter, the Co-I will approach his/her patient and as part of the anesthesia consent process will explain that the Co-I will need to place a peripheral intravenous catheter, so that the patient can receive anesthesia during the operation. While obtaining consent for anesthesia, the Co-I will identify if the patient fits the inclusion criteria for the study and does not meet any of the exclusion criteria. If the patient does satisfy the inclusion criteria, then the Co-I will explain that insertion of a peripheral intravenous catheter may cause some discomfort. The Co-I will explain that some providers at this institution choose to administer the peripheral intravenous catheter without any pain preventative techniques while some choose to inject a numbing medication under the skin prior to the placement of the peripheral intravenous catheter. Also, some providers at other institutions use the Buzzy® device, which is a combination of an ice pack and a vibrator in the shape of a bumble bee, to place a peripheral intravenous catheter on children. This device is FDA approved. There is significant literature documentation that this Buzzy® device helps children feel less pain with peripheral intravenous catheter placement; however, the Buzzy® device has not been utilized that much in adult patients. The Co-I will explain that we are conducting a study to compare the effectiveness of Buzzy® device to that of the injection of the numbing medication under the skin. The Co-I will then ask

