whether the patient may be interested in learning more about the study and potentially partaking in the study. If the patient says yes, then the Co-I will go over the consent form with the patient and explain that if the patient chooses to partake in the study, then he/she will randomly receive either the Buzzy® device or the numbing injection. The Co-I will answer any questions that the patient may have. If the patient consents to partaking in the study, then the Co-I will follow the randomization sheet with which pain-relieving technique to be administered to the patient. The Co-I will administer the appropriate technique and place the peripheral intravenous catheter.

Specifics of how the two interventions will be performed:

Experimental group - *Buzzy® device*: Subjects in this group will have the Buzzy® device applied to them. The Buzzy® consists of two components: (1) body of the bee, which provides vibration, and (2) removable and reusable ice wings, which provide the cold sensation. The body of the bee is powered by two alkaline AAA batteries, which could last for approximately 20 hours. There is a manual switch on the top part of the body of the bee that is used to activate and deactivate the vibration. The removable set of ice wings contain a total of 18 grams of ice and can stay frozen for about 10 minutes when exposed to room temperature. The Co-I who will be applying the Buzzy® device will follow the manufacturer's (MMJ Labs, Atlanta, Georgia, USA) recommendations and will (1) retrieve the set of ice wings from the freezer in the Preop Unit immediately before the peripheral intravenous catheter procedure, (2) insert the ice wings through the elastic bands fixed on the back of the Buzzy® device, (3) secure the Buzzy® device on the subject's arm with a reusable tourniquet, about 3-5cm proximal to where the peripheral intravenous catheter will be inserted, (4) turn the manual switch of the device on, (5) clean and prepare the area where the peripheral intravenous catheter will be inserted, (6) insert the peripheral intravenous catheter approximately 60 seconds after the Buzzy® device was applied, (7) keep the device turned on throughout the procedure, until at least the needle is removed, (8) remove the Buzzy® device and clean both components of the device (body of bee and ice wings) with a disinfectant cleaner, (9) and place the ice wings back in the freezer of the unit for a subsequent procedure.

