Will biological specimens be stored for future, unspecified, research?

Yes No

G. Ethics and Protection of Human Subjects

G.1 Informed Consent Process

Will subjects be required to provide informed consent?

Yes No

If Yes, respond to all of the following:

1. *Where the consent process will take place (e.g. a private clinic room):* In the preoperative room.
2. *Anticipated amount of time a potential subject will have to make a decision about participation in the study:* About 5 minutes
3. *Processes to ensure ongoing consent throughout the study:* The PI will randomly observe the investigators obtaining consent to ensure that the consent continues to be done properly.

4. **Role of each research team member involved in the informed consent process (please note, for a biomedical study, a physician PI or Co-I should perform the informed consent process with subjects. A study coordinator may assist with this process; however, the PI or Co-I should be present to discuss the study with the subject and answer any questions, and the PI or Co-I should sign the ICF documenting that s/he has performed the informed consent process with the subject):** The PI (anesthesiology attending) and Co-I's (anesthesiology residents) of the study will be the ones that will be taking care of the subjects. They are the ones that will be consenting subjects for the study. They are all experienced in consenting patients because they do that on a daily basis, as part of their job, prior to administering anesthesia. The PI and Co-Is will not be at an increased risk to COVID-19 because of this study because the study members will be the ones who will be taking care of the subjects while the subjects are getting the peripheral intravenous catheter insertion and later on when the subjects will be receiving anesthesia for the scheduled surgeries, regardless whether the subjects choose to partake in this study.
5. *Check to confirm you will follow “[SOP: Informed Consent Process for Research \(HRP-090\)](#)”.*
If not, answer all of the following:
 - a. *Steps that will be taken to minimize the possibility of coercion or undue influence:*
 - b. *Steps that will be taken to ensure subjects' understanding:*

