 - b. *Where and how data or specimens will be stored:* Data will be stored in a locked cabinet in the PI's office (as described above).
 - c. *How long the data or specimens will be stored:* Data will be stored at least until the results of the study will be published.
 - d. *Specify who will have access to the data or specimens:* The Research team will have access to the data.
 - e. *Specify who is responsible for receipt or transmission of the data or specimens:* The PI will be responsible for the receipt of the data.

- f. **Specify how data and specimens will be transported:** Data will be transported in a closed envelope from the preoperative area and to the PI's office, where it will be stored in a locked cabinet. If data will need to be transferred between research team members for statistical analysis purposes, the word [SECURE] will be included in the subject line of all emails.
- g. **Specify the plan for study data retention and storage (accounting for research team turnover):** Data will remain secure in the PI's office, in a locked cabinet.

I.5 Randomization

Will subjects be randomized?

Yes No

If Yes respond to all of the following:

1. **Describe the randomization procedures, including the ratio of subjects randomized to each study arm:** We will use <http://www.graphpad.com/quickcalcs/index.cfm> to generate a randomized sequence, with a ratio of subjects 1:1 in each arm. <https://www.ncbi.nlm.nih.gov/pmc/articles/PMC3136079/>
2. **Describe the blinding procedures:** The Co-I's that will be conducting the statistical analysis will be blinded to which study arm the subjects were assigned to. N/A the study will not be blinded.

J. Drugs or Devices

1. Will the research involve drugs?

Yes No

If Yes, respond to all of the following:

- a. **If the drug is investigational (has an IND) identify the holder of the IND:** The drug, Lidocaine 2%, is not an investigational drug. It is a commonly used drug that is widely available.
- b. **Describe your plans to store, handle, and administer study drugs so that they will be used only on subjects and be used only by authorized investigators** N/A - this drug is used throughout the hospital for many procedures.
- c. **Who on the research team, in addition to the Principal Investigator, will be accountable for drug(s):** The PI and the Co-Is have access to Lidocaine 2% when they are interacting with patients.

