- f. *Who on the research team, in addition to the Principal Investigator, will be accountable for device(s):* The co-investigators.
- g. *Who will interface with the sponsor:* N/A
- h. *The study device or procedure (including beneficial health care procedures) will be available to subjects after participation in the study:* Yes N/A
- i. *Handouts or instructions sheets that will be given to subjects on how to use study device(s) have been submitted to the IRB:* Yes N/A

K. Study Administration

K.1 Setting

1. *Describe the sites / locations where your research team will conduct the research:* St. Elizabeth's Medical Center
2. *The research will take place at an international site, and the International Guidance and International Checklist were utilized:* Yes N/A

K.2 Registration

1. *Describe the steps the research team will take to ensure that a subject is appropriately enrolled or registered in the study prior to receiving any study intervention (e.g. describe and submit any protocol eligibility checklist that will be used, specify who on the research team will confirm eligibility and that consent was documented, etc.):* Enrollment into the study will be very shortly after the consent process, so the Co-I who will be obtaining consent will not start performing any procedure until he/she obtains the consent.

K.3 Resources Available

1. *Describe the roles/tasks of each research team member here (or alternatively, you may submit any current Delegation of Authority Log you may have which already has this information completed):* The Co-investigators will be enrolling subjects into the study and will be the ones who will be administering the treatment and collecting data. The PI and the Co-I's will be performing the statistical analysis and reviewing each others computations to ensure accuracy.
2. *Describe the qualifications (e.g., training, experience) of the PI and research team to perform their roles. Provide enough information for the IRB to determine the PI and research team are qualified to conduct the proposed research. Alternatively, you can submit the current CVs for the research team instead:* The PI is an anesthesiology attending at St. Elizabeth's Medical Center. The Co-I's are second year anesthesiology resident physicians (aka CA-1's). They have all at least completed medical school training and one year of residency. They are all qualified to obtain consent from patients and have significant experience doing so.

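### F.2 and I.5 describe nothing that keeps the next assignment from the Co-I who screens, consents and treats the patient.

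*Combined protocol and SAP*

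**What the plan says.** **Generation.** I.5, item 1, names an online tool used "to generate a randomized sequence, with a ratio of subjects 1:1 in each arm", followed by a bare link to an article. It gives no list holder and no means of releasing one assignment at a time.

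**Use.** F.2 says that after consent "the Co-I will follow the randomization sheet with which pain-relieving technique to be administered to the patient".

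**Who does what.** In F.2 the Co-I finds candidates on the operating room schedule: "If the patient does not yet have a working peripheral intravenous catheter, the Co-I will approach his/her patient". During anesthesia consent, "the Co-I will identify if the patient fits the inclusion criteria for the study and does not meet any of the exclusion criteria". The Co-I then explains the study, takes consent, applies the assigned technique and places the catheter. K.3 confirms that the Co-Is enroll, treat and collect data. D.2, item 3, has the PI and Co-I determine eligibility and says "These will be the physicians who will be taking care of these subjects". G.1 says of the PI and Co-Is: "They are the ones that will be consenting subjects for the study".

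**Order of steps.** K.2 adds that "the Co-I who will be obtaining consent will not start performing any procedure until he/she obtains the consent".

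**Eligibility.** The first exclusion in D.2 is "Patients with Raynaud's syndrome, sickle cell disease, and/or extreme sensitivity to cold".

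**Envelopes.** Those in F.2 and I.4 carry completed questionnaires and data, not assignments.

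**Numbers.** I.3 aims for 30 completers and allows up to 40 enrolled.

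**The concern.** Random generation and concealment are separate safeguards. A properly random list can still be read ahead by whoever holds it. Here the person who consults the list is also the person who decides whether a patient qualifies and how the study is presented. Once a multi-line sheet has been used for one patient, the lines below may already have been seen.

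Most of the D.2 criteria leave little room for discretion: Raynaud's syndrome and sickle cell disease are diagnoses, and broken skin can be observed. Marked cold sensitivity is a matter of judgment, and it bears only on the Buzzy arm. How warmly the study is offered is also discretionary. If the next arm is known, either could differ by arm, and the two groups would then differ before any treatment is given.

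What is at stake is baseline comparability. The planned t-test and chi-square test contain no adjustment. Even an adjusted analysis could correct only for traits that were recorded, so analysis cannot fully replace concealment.

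**Working it through.** **1. Is concealment described anywhere?** The claim concerns missing text, so the relevant sections are set side by side.

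| Section | What it fixes | Does it hide the next arm? |
|---|---|---|
| D.2, items 2 and 3 | Eligibility from the pre-operative history and examination, by PI and Co-I | No |
| F.2 | Eligibility, then consent, then sheet | No; sets an order for one patient |
| G.1 | PI and Co-Is take consent | No |
| I.5, item 1 | Web tool, 1:1 ratio, article link | No |
| I.5, item 2 | Statement about blinded analysts, beside text saying the study will not be blinded | No; acts after assignment |
| K.2 | Consent before any procedure | No; silent on access to the sheet and on recording eligibility first |
| K.3 | Co-Is enroll, treat and collect data | No |

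Whether a screening log is used (G.5) cannot be read, because the tick-box is lost.

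**2. How large could a bias be?** The plan has no figure to reproduce here: it gives no SD, effect size or margin. From the plan come 30 completers at 1:1, hence 15 per arm, and P < 0.05. The sidedness of the pilot's own test is not stated; two-sided is assumed. Every other input below is assumed.

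Standard error of the difference in means, in SD units: √(2/15) = 0.365. The false-positive rate is the rejection rate of a two-sided 5% t-test with 28 degrees of freedom (noncentral t) when there is no true difference.

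*(a) The Buzzy-only criterion.* Borderline cold-sensitive patients are excluded only when Buzzy is next. Bias = s × f × d, where s is the share of Buzzy slots affected, f the borderline fraction and d their difference in pain in SD. The documents do not link cold sensitivity to cannulation pain, so d may be 0.

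| s | f | d | Bias (SD) | Bias/SE | False-positive rate |
|---|---|---|---|---|---|
| any | any | 0 | 0 | 0 | 5.0% |
| 0.5 | 0.05 | 0.5 | 0.0125 | 0.03 | 5.0% |
| 0.5 | 0.20 | 0.5 | 0.05 | 0.14 | 5.2% |
| 1 | 0.20 | 0.5 | 0.10 | 0.27 | 5.8% |

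Borderline patients missing from a Buzzy arm of 15 number 15 × s × f: from 15 × 0.5 × 0.05 = 0.4 to 15 × 1 × 0.20 = 3.

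*(b) General steering on visible traits.* A fraction q with the most extreme trait values is passed over in a share s of one arm's slots; the trait correlates r with pain. Bias = s × r × φ(z)/(1 − q), with z the (1 − q) normal quantile. For q = 0.3, z = 0.524 and φ(z) = 0.348, so φ(z)/(1 − q) = 0.497. With r = 0.5 the bias is 0.5 × 0.5 × 0.497 = 0.124 for s = 0.5, and twice that, 0.248, for s = 1.

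| s | r | q | Bias (SD) | Bias/SE | False-positive rate |
|---|---|---|---|---|---|
| 0.5 | 0.3 | 0.1 | 0.029 | 0.08 | 5.1% |
| 0.5 | 0.5 | 0.2 | 0.087 | 0.24 | 5.6% |
| 0.5 | 0.5 | 0.3 | 0.124 | 0.34 | 6.2% |
| 1 | 0.5 | 0.3 | 0.248 | 0.68 | 10.1% |

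The last two rows differ only in the share of slots affected, and nothing in the documents favors one over the other. The top of the range therefore reflects the inputs chosen and is not a ceiling.

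**The case against.** **The written order already protects.** Eligibility rests on the pre-operative history and examination, is identified before the study is introduced, and comes before consent; only then is the sheet followed. F.2 is also directive about approaching the patient. Steering would need someone to look at the sheet ahead of its place in the sequence. This stands as a narrowing of the gap. It does not close it, because an order of steps for one patient does not cover the line for the next.

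**The documents do not show an open sheet.** Correct. A reader might infer that Co-Is see upcoming assignments, or that enrollment will be steered. Neither is stated. The form's question in I.5 asks for procedures and ratio and does not mention concealment, and the linked article cannot be read here. Still, a bare link does not state this trial's procedure.

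**Open treatment and self-rated pain.** A reader might infer that concealment would deal with the bias these create. It would not. Expectation and reporting bias arise after assignment and remain even with perfect concealment.

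**It is a pilot, and the effect may be nil.** This stands as to size. No harm to the sizing of the later trial is shown. But I.2 still applies a significance threshold, so comparable arms matter for the comparison as planned.

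**Conclusion.** The concern holds in limited form. The plan has the recruiting and treating Co-I work from a randomization sheet and describes nothing that keeps later lines from that person, in a trial with one exclusion that is partly a judgment and relevant to one arm only. That the text is missing is certain, apart from what the unread link might say. That any bias will follow is not.

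Its size is unknown. Illustrations run from 0 to about 0.25 SD, up to about 0.7 of a standard error with 15 per arm, and a false-positive rate of 5% to about 10%. They rest entirely on assumed fractions, correlations and shares of affected slots. The case for change does not depend on the upper figure: the safeguard is cheap, and once enrollment has taken place the analysis cannot fully stand in for it. It is a worthwhile improvement to the method, not evidence that the trial's results will be wrong.

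**What to change.** - **F.2 and I.5:** replace the sheet with about 40 sequentially numbered, opaque, sealed envelopes (the enrollment cap is 40), prepared from the generated list by a person who does not screen, consent or treat. Open them strictly in order.
- **K.2:** add a step under which an envelope is opened only after the consent form is signed and eligibility is recorded.
- **Log:** record every opened envelope, including those of subjects who then change their mind. I.3 foresees this happening while the catheter insertion is being prepared, when the arm may already be known.
- **K.3:** name the preparer's role. If it is the PI, align D.2 and G.1, which now give the PI a share in eligibility and consent. If it is someone else, that person must be on the research team, because G.4 limits access to study files to the team.

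The cost is one preparation of envelopes, a short log and wording in these sections. Sample size, study procedures and analysis do not change.

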QUESTIONNAIRE

[figure not shown]
Questions to be answered by the Research Team:

Buzzy vs Intradermal Lidocaine for Peripheral Intravenous Cannulation in Adults

QUESTIONNAIRE

Questions to be answered by the Patient:

1) Please circle a number 0 to 10 in regard to how painful was the IV placement?

2) Please circle how satisfied you are with the IV placement?

Very Dissatisfied	Dissatisfied	Neither Satisfied nor Dissatisfied	Satisfied	Very Satisfied
(1)	(2)	(3)	(4)	(5)
				

2. *Is there a placebo control arm?*

Yes No

1. *Describe the following concerning pregnancy testing and birth control:*

- a. *What type of pregnancy testing and how frequently will be conducted on women of reproductive potential. If testing will not be conducted provide the reason:* N/A
- b. *What birth control methods women of reproductive potential will be instructed to use. If women will not be instructed about acceptable methods of birth control, clarify why:* N/A
- c. *What birth control methods men of reproductive potential will be instructed to use. If men will not be instructed about acceptable methods of birth control, clarify why:* N/A

2. *Describe the data that will be collected during the study and how the data will be obtained:*

- a. *If there are plans for long-term follow-up (once all research related procedures are complete), describe the data will be collected during this period:* or N/A

3. *Specify which procedures, tests, visits, etc. described above are part of usual standard of care at Tufts and which are performed solely for research purposes:* Insertion of intravenous catheter is part of the usual standard of care. The use of the Buzzy® device is not part of the current standard of care in adult patients at SEMC.

4. *Specify which tests are routinely performed for clinical care, but are providing data for the research, and which tests are only performed for research purposes:* No tests will be performed for the purposes of this study.

5. *For Humanitarian Use Device (HUD) uses provide a description of the device, a summary of how you propose to use the device, including a description of any screening procedures, the HUD procedure, and any patient follow-up visits, tests or procedures.* or N/A

F.3 Evaluations

Will you perform any laboratory tests for this study?

Yes No

F.4 Collection and Storage of Human Biological Specimens (Tissue Banking)

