4. **Can or will minors who are:**

- i) married, widowed, divorced; or
- ii) the parent of a child; or
- iii) a member of any of the armed forces; or
- iv) pregnant or believes herself to be pregnant; or
- v) living separate and apart from his/her parent or legal guardian, and is managing his/her own financial affairs

be approached for study participation for either themselves or their child?

Yes No

5. **Can or will wards of the state and/or children at risk of becoming wards of the state be enrolled (this includes foster children or any child that is in state custody)?**

Yes No

6. **Can or will cognitively impaired adults (adults with impaired-decision making capacity) or adults who may lose the capacity to consent be enrolled?**

Yes No

7. **Can or will prisoners be enrolled?**

Yes No

8. **Can or will students and/or employees be targeted for enrollment in this research?**

Yes No

9. **Transgender Subjects: Are you recording sex or gender for your study?**

Yes No

a. Is there a scientific and/or safety rationale for collecting information on whether a subject is transgender? Yes No

If **Yes**, respond to all of the following:

- i. **Provide the scientific/safety rationale for collecting information on whether a subject is transgender:** We do not want to exclude subjects from enrolling into the study based on sex or gender. We feel it is important to know whether the sex of the subject because that could be a confounding variable in terms of how one describes anxiety, pain, and satisfaction.
- ii. **Are transgender individuals eligible for participation in this study?** Yes No
If **No**, *Provide the scientific or safety rationale for excluding transgender or gender nonconforming individuals:*
- iii. **Check to confirm that relevant questions for transgender and gender nonconforming individuals have been incorporated into relevant study documents (i.e. protocol eligibility, screening forms, demographic questionnaires, surveys), per the [website guidance](#).**

H. Adverse Event Monitoring

H.1 Definitions

Define adverse events (AEs), serious adverse events (SAEs), and unanticipated problems for your study:
N/A

H.2 Reporting Procedures

1. *Describe the protocol-specific reporting procedures, including who will be responsible for each step (e.g., PI, Data Coordinating Center, Medical Monitor), which forms should be completed, timeframes for reporting, how reports will be distributed, and what follow-up is required:* N/A

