2. *Include specific details of reporting procedures for:*
 - a. Deaths, life-threatening events, pregnancies: N/A
 - b. Other SAEs: N/A
 - c. Other AEs: N/A
 - d. Other UPS: N/A

H.3 Reportable New Information

Check to confirm that reportable new information will be reported to the IRB per the Tufts Health Sciences IRB's [Reportable New Information policy](#). If your reporting plan to the IRB differs from the IRB's policies, please describe it in detail or specify where this information is in the protocol:

I. Statistical Considerations

I.1 Study Endpoints

1. *Describe the primary and secondary study endpoints:* Primary study endpoint: Pain rating of the peripheral intravenous catheter insertion; Secondary study endpoint: Satisfaction rating of the peripheral intravenous catheter insertion
2. *Describe any primary or secondary safety endpoints:* N/A

I.2 Statistical Analysis

1. *Describe the statistical analyses that will be performed for this study:* Continuous variables will be analyzed via the Student's t-test and presented as mean +/- standard deviation. Categorical data will be analyzed via Chi-square test and presented as number and percentages. The intention-to-treat analysis will be used in this study. A P-value <0.05 will be considered statistically significant.
2. *Provide a power analysis:* Since there is currently no published study available comparing the two interventions that we plan on studying, we chose the study sample size based on the sample size rule of thumb for medical trials.¹³ The purpose of this study is to conduct a preliminary pilot trial for a potential future main trial designed with 90% power and two-sided 5% significance.

I.3 Number of Subjects

1. *Specify the number of subjects to be enrolled in total across all sites:* or N/A this is not a multicenter study.
2. *Specify the number of subjects to be enrolled at the Tufts site. Subjects who sign an ICF are considered “enrolled”. For studies that have a separate screening ICF, this number is the number of subjects who sign a screening ICF:* The goal will be to have a total of 30 subjects sign an ICF and complete the study based on the previously published sample size rule of thumb for medical trials.¹³

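### Sex is named as a possible confounder of pain and satisfaction ratings but has no stated role in the arm comparison; one prespecified covariate would be a cheap improvement

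*Combined protocol and SAP*

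**What the plan says.** G.8 item 9(a)(i) asks why information on transgender status is collected. The answer gives this reason: "We feel it is important to know whether the sex of the subject because that could be a confounding variable", and it names reported anxiety, pain and satisfaction as what sex could affect. Section I.1 then lists "Primary study endpoint: Pain rating of the peripheral intravenous catheter insertion", with the satisfaction rating as the secondary endpoint. The patient half of the questionnaire in F.2 records pain on a 0 to 10 scale ("Please circle a number 0 to 10 in regard to how painful was the IV placement") and satisfaction in five ordered categories.

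Section I.2 item 1 gives the whole analysis: "Continuous variables will be analyzed via the Student's t-test and presented as mean +/- standard deviation", a chi-square test for categorical data, intention to treat, and "A P-value <0.05 will be considered statistically significant". It names no covariate, adjusted model, subgroup or sensitivity analysis. Section I.5 describes a 1:1 random sequence and no stratification. Section I.3 aims for 30 subjects completing the study.

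**The concern.** The protocol singles out one baseline factor as likely to influence how subjects rate both endpoints, and then does not say what the analysis will do with it. With about 15 subjects per arm, randomization does not reliably balance a binary factor. If one arm has more women and women rate pain differently, part of the observed difference between techniques comes from that imbalance.

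Two features of the plan make a stated rule worth having. The investigators run the analysis themselves (F.2, K.3), so without one, whether to adjust could be decided after an imbalance is seen. And the background section says the results may be used to size a later non-inferiority trial, which would benefit from knowing how much of the pain variation is due to sex.

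**Working it through.** **The plan's own figure.** The target of 30 cannot be re-derived. The documents give no effect size, SD or margin, and the rule of thumb is in a cited source. Section I.2 mentions a "potential future main trial designed with 90% power and two-sided 5% significance", but that describes the later trial. The check therefore starts from 30 completers at 1:1, taken as 15 per arm.

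**Assumptions (none is in the documents).** Share of women 50% (range 30 to 70%); sex gap in mean pain 1 point (range 0.5 to 1.5); SD of pain 2 to 2.5 points; two-sided test at 5%.

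**Step 1: how often the arms differ.** Let X1 and X2 be the numbers of women per arm, independent Binomial(15, 0.5). The SD of the difference in proportions is sqrt(2 × 0.25/15) = 0.183, or 18 percentage points. Exactly:
- at least 3 women (20 points): 0.362
- at least 4 women (27 points): 0.200
- at least 5 women (33 points): 0.099

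With 30% or 70% women, the figures for 3 and 5 women are 0.318 and 0.071.

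**Step 2: what an imbalance does.** Shift = imbalance in proportion × sex gap. For 3 women and a 1-point gap: 3/15 × 1 = 0.2 point (0.1 to 0.3 for gaps of 0.5 to 1.5).

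The standard error of the arm difference is SD × sqrt(2/15) = 0.365 × SD, that is 0.73 at SD 2 and 0.91 at SD 2.5. So 0.2 point is 0.2/0.73 = 0.27 SE or 0.2/0.91 = 0.22 SE. For 5 women the shift is 0.33 point, or 0.37 to 0.46 SE.

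**Step 3: is the t-test still valid?** A simulation used 100,000 trials per setting, 15 v 15, 50% women and sex effects from 0 to 1.0 within-sex SD. Averaged over randomizations, the unadjusted difference was within 0.003 SD of the truth. Type I error was 0.049 to 0.051 unadjusted and 0.048 to 0.051 adjusted.

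The unadjusted rate departs from 5% only when conditioned on an imbalance. With at least 5 more women in one particular arm (about 5% of trials), it is 0.076 for a sex effect of 0.5 SD and 0.135 for 1.0 SD, against about 0.05 adjusted.

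**Step 4: what adjustment costs or gains.** Approximate variance ratio, adjusted to unadjusted: (1 − R²) × 27/26, with R² = gap² × 0.25/SD².

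| Gap (points) | SD | R² | Variance ratio |
|---|---|---|---|
| 0 | any | 0 | 1.038 |
| 0.5 | 2.5 | 0.010 | 1.028 |
| 1 | 2.5 | 0.040 | 0.997 |
| 1 | 2 | 0.063 | 0.974 |
| 1.5 | 2 | 0.141 | 0.892 |

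The simulation agrees at zero effect: (0.373/0.366)² = 1.039. Break-even is R² = 1/27. For a gap of b within-sex SDs, b²/4 = 1/26, so b = sqrt(4/26) = 0.39.

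Simulated power at a true difference of 1 SD, unadjusted v adjusted, was 0.745 v 0.735 (sex effect 0.25 SD), 0.727 v 0.738 (0.5 SD), 0.688 v 0.735 (0.8 SD) and 0.657 v 0.735 (1.0 SD).

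**The case against.** The strongest reply is that chance imbalance under randomization is random error. The t-test's standard error already contains the variation between the sexes, so the test needs no repair. This stands. A reader might infer from the word confounding in G.8 that the unadjusted comparison is biased or its P-value unreliable; step 3 shows neither.

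The size is also modest. At SD 2 to 2.5 the 95% half-width is about 2.05 × 0.73 = 1.5 to 2.05 × 0.91 = 1.9 points, so a 0.2-point shift is 11 to 13% of it. At the central 1-point gap the variance falls by 3% at most, and at 0.5 point adjustment loses a little. An unadjusted analysis is defensible in a 30-subject pilot.

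A reader might also infer that sex is collected and then ignored. The documents do not show that. The chi-square sentence in I.2 could cover a descriptive table of sex by arm, and nothing says sex will go unreported. The G.8 sentence answers an ethics-form item, says only that sex could matter, and also names anxiety, which neither visible patient question measures. It is not an analysis commitment that I.2 breaks. Whether sex is recorded at all cannot be confirmed here, because the checkbox marks and the research-team half of the questionnaire are not visible.

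Finally, I.5 contains wording that the analysts will be blinded to arm, which would limit a selective choice about adjustment. The same item also carries an option saying the study is not blinded, and which was ticked is lost. Even coded arms would show an imbalance, so a rule set in advance still helps.

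**Conclusion.** The point holds as a gap in specification: the protocol gives a reason to care about sex, and I.2 and I.5 give it no role in the comparison. It does not hold as a claim of bias or inflated type I error.

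The consequence is conditional. In roughly one randomization in three (0.32 to 0.36 for 30 to 70% women) the arms differ by 3 or more women. Three women shift the observed difference by about a quarter of a standard error per 1-point sex gap, and larger imbalances shift it more. Adjustment removes that shift, but improves average precision only if the sex gap exceeds about 0.39 SD. The sex gap, the SD, the share of women and the exact 15/15 split are all assumptions. This is a cheap improvement, not a necessary correction.

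**What to change.** In I.2, add a linear model of pain score on arm and sex, reporting the sex-adjusted Buzzy-minus-lidocaine difference with its confidence interval beside the t-test. State in advance whether it is the primary analysis or a named sensitivity analysis; either closes the gap. Report sex by arm.

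Do the same for satisfaction if it is analysed as a continuous score; I.2 should say whether that five-category item is treated as continuous or categorical. Confirm that the research-team half of the questionnaire records sex, since I.4 limits the data to what the questionnaire contains.

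The cost is a sentence or two and one degree of freedom. The average variance change runs from about a 4% increase if sex has no effect to about an 11% reduction at a 1.5-point gap and SD 2.
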